## 5. Population

This study will be conducted in adult patients with relapsed FL or who are refractory (not anti-CD20 antibody refractory) and have received one or more prior therapies, including anti-CD20 therapy.

#### 5.1. Inclusion Criteria

Patients are eligible to be included in the study only if all of the following criteria apply:

- 1) Patient must be  $\geq$ 18 years at the time of signing the informed consent
- 2) A pre-study Eastern Cooperative Oncology Group (ECOG) performance status of 0-2
- 3) Histologically confirmed diagnosis (by 2008 World Health Organization [WHO] classification) of indolent non-Hodgkin B-cell FL (grade 1, 2 or 3a)
- 4) At least one (but not more than 3) prior regimens with an anti-CD20 antibody (alone or in combination with chemotherapy), with documented relapsed, refractory disease (must not be anti-CD20 antibody-refractory) or PD
- 5) Presence of at least one bi-dimensionally measurable lesion by CT or MRI: longest diameter (LDi) >1.5 cm for a nodal lesion; LDi >1.0 cm for an extranodal lesion within 28 days prior to start of treatment
- 6) Normal organ and bone marrow function defined as:
  - a. Absolute neutrophil count  $\geq 1.5 \times 10^9/L$ ;
  - b. Platelet count  $\geq 150 \times 10^9 / L$ ;
  - c. Haemoglobin ≥9 g/dL;
  - d. Total bilirubin ≤1.5 x upper limit of normal (ULN) (except patients with documented Gilbert's syndrome [<3.0 mg/dL]);
  - e. Liver enzymes: Aspartate transaminase (AST); Alanine transaminase (ALT) or Alkaline phosphatase (ALP) ≤2.5 x ULN (or ≤5.0 x ULN if liver involvement by primary disease);
  - f. Adequate renal function as demonstrated by a serum creatinine within the upper limit of normal range
- 7) Bone marrow involvement by lymphoma <25%
- 8) Life expectancy >3 months
- 9) Negative hepatitis B, hepatitis C and human immunodeficiency virus (HIV) screening tests
- 10) Undetectable human anti-murine antibody (HAMA) at screening
- 11) Women of childbearing potential (see Appendix 3) must:
  - a. have a negative serum pregnancy test at screening
  - b. understand that the study medication is expected to have teratogenic risk
  - c. agree to use, and be able to comply with, highly effective method of birth control with a Pearl-Index  $\leq 1\%$

Contraception is required without interruption, from 4 weeks before starting study drug, throughout study drug therapy and for 12 months after end of study drug therapy, even if she has amenorrhea

12) Male patients must agree to use condoms (See Appendix 3) during intercourse throughout study drug therapy and for 12 months after end of study drug therapy

- 13) The patient is willing and able to comply with the protocol, and agrees to return to the hospital for follow-up visits and examination
- 14) Capable of giving signed informed consent which includes compliance with the requirements and restrictions listed in the informed consent form (ICF) and in this protocol

#### 5.2. Exclusion Criteria

Patients are excluded from the study if any of the following criteria apply:

- 1) Previous haematopoietic stem cell transplantation (autologous and allogenic)
- 2) Evidence of histological transformation from FL to DLBCL at time of screening.
- 3) Previous total body irradiation
- 4) Chemotherapy, immunotherapy or investigational therapy within 28 days before the start of study drug administration (corticosteroid treatment at doses of ≤20 mg/day, topical or inhaled corticosteroids, granulocyte colony-stimulating factor [G-CSF] or granulocyte-macrophage colony-stimulating factor [GM-CSF] are permitted up to 2 weeks prior to start of study treatment) or failure to recover from AEs associated with prior treatment
- 5) Previous treatment with radioimmunotherapy
- 6) Patients who are receiving any other investigational medicinal products
- 7) Known or suspected central nervous system (CNS) involvement of lymphoma
- 8) History of a previous treated cancer except for the following:
  - a) adequately treated local basal cell or squamous cell carcinoma of the skin
  - b) cervical carcinoma in situ
  - c) superficial bladder cancer or localised prostate cancer undergoing surveillance or surgery
  - d) localised breast cancer treated with surgery and radiotherapy but not including systemic chemotherapy
  - e) other adequately treated Stage 1 or 2 cancer currently in CR
- 9) Pregnant or lactating women (See Appendix 3)
- 10) Exposure to another CD37 targeting drug
- 11) A known hypersensitivity to RTX, lilotomab, Betalutin or murine proteins or any excipient used in RTX, lilotomab or Betalutin
- 12) Receipt of live, attenuated vaccine within 30 days prior to enrolment
- 13) Evidence of severe or uncontrolled systemic diseases:
  - a. Uncontrolled infection including evidence of ongoing systemic bacterial, fungal, or viral infection (excluding viral upper respiratory tract infections) at the time of initiation of study treatment
  - b. Pulmonary conditions e.g. unstable or uncompensated respiratory disease
  - c. Hepatic, renal, neurological, or metabolic conditions which in the opinion of the Investigator would compromise the protocol objectives

**CONFIDENTIAL** 

- d. Psychiatric conditions e.g. patients unlikely to comply with the protocol, e.g. mental condition rendering the patient unable to understand the nature, scope, and possible consequences of participating in the study
- e. History of erythema multiforme, toxic epidermal necrolysis or Stevens-Johnson syndrome
- f. Cardiac conditions, including:
  - i. history of acute coronary syndromes (including unstable angina)
  - ii. class II, III or IV heart failure as defined by the New York Heart Association (NYHA) functional classification system
  - iii. known uncontrolled arrhythmias (except sinus arrhythmia) in the past 24 weeks

## 6. Study Treatment

For this study, the term "study drug(s)" refer to RTX, lilotomab or Betalutin.

RTX, lilotomab and Betalutin can all be administered on an outpatient basis, dependent on local regulations. The patient should be under surveillance at the clinic/hospital for at least 2 hours after administration (unless local regulations require a longer surveillance period).

Detailed written instructions on labelling and preparation will be given to the study site prior to patient inclusion. See also Investigator's Brochure and RTX prescribing information.

## 6.1. Dosing regimen

Two cohorts of 3-6 patients will initially be evaluated. The first cohort of 3 patients will be treated with a single i.v. dose of RTX (375 mg/m²) on Day -14, and then on Day 0, sequential i.v. administration of lilotomab (40 mg) followed by Betalutin (10 MBq/kg) within 4 hours on Day 0. The patients will then be administered RTX (375 mg/m²) i.v. on Days 7, 14, 21 and 28.

Patients must have received all doses of study drug and have had an adequate period of follow-up (i.e. having achieved haematological recovery to  $\leq$  grade 2) to be considered evaluable for a dose escalation decision or to determine the dose for further Phase 2 studies following enrolment of the second cohort of 3-6 patients. The dose for the next cohort of 3 patients will be determined by the Investigator(s) and Nordic Nanovector study personnel via teleconference. Decisions will be based on a review of all safety data (clinical and laboratory) and are outlined as follows:

- 1. If 0/3 patients experience a DLT (defined below), the next cohort of 3 patients will receive lilotomab 40 mg plus Betalutin 15 MBq/kg prior to RTX on Day 0.
- 2. If 1/3 patients experience a DLT, then 3 more patients will be enrolled in the current cohort at this dose level (Betalutin 10 MBq/kg).
- 3. If 2/3 patients experience a DLT, then subsequent Betalutin/lilotomab and/or RTX dosing will be determined by the Investigator(s) and Sponsor after a review of the safety data.
- 4. If 1/6 patients experience a DLT, the next cohort of 3 patients will be treated with Betalutin 15 MBq/kg.
- 5. If 0/3 patients receiving Betalutin 15 MBq/kg experience a DLT, the remainder of the patients in the study will continue to be treated with Betalutin 15 MBq/kg.
- 6. If 1/3 patients experience a DLT, then 3 more patients will be enrolled at this dose level (Betalutin 15 MBq/kg).
- 7. If 1/6 patients receiving Betalutin 15 MBq/kg experience a DLT, the dose for further Phase 2 studies will be Betalutin 15 MBq/kg.
- 8. If 2/6 patients experience a DLT, then 3 more patients will be treated at the lower Betalutin dose (10 MBq/kg).
- 9. The final recommendation for Betalutin/lilotomab dosing for further Phase 2 studies will be determined by the Investigator(s) and Sponsor after a review of the available safety data.

DLT is defined as:

**Haematological:** Anemia, neutropenia or thrombocytopenia CTCAE (v4.03) grade 4 lasting >7 days, or grade 3 thrombocytopenia with clinically significant bleeding, or febrile neutropenia (ANC <1000/mm^3 with a temperature >38.3°C).

**Non-haematological**: An AE of CTCAE (v4.03) grade 3 or higher where the relationship to study treatment cannot be ruled out, and is not primarily related to disease, disease progression, intercurrent illness or concomitant medications that occurs within the first 12 weeks of treatment. Other clinically significant toxicities may also be considered to be DLTs by the Investigators and Sponsors, even if not CTCAE grade 3 or higher.

Responding patients (i.e. those having a CR, PR or SD response following Betalutin and the 4-weekly doses of i.v. RTX) will receive maintenance RTX every 3 months for up to 2 years (a total of 8 doses), or until disease progression, commencing at Week 14. This may be administered by either i.v. (375 mg/m²) or s.c. (fixed dose of 1400 mg) routes.

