With a lilotomab pre-dose of 40 mg (Arm 1), the recommended dose of Betalutin for phase 2 expansion was 15 MBq/kg. In total, 36 patients have received this regimen (25 with FL); the overall response rate (ORR) is 64% (CR 25%), and 72% (CR 24%) for the FL subset, and the toxicity profile is favourable. The incidence of grade 3/4 neutropenia and thrombocytopenia was 20/36 (56%) for both. Grade 4 neutropenia and thrombocytopenia were reported in 7 patients (19%) and 6 patients (17%) respectively. Of these, there were 2 patients with grade 4 neutropenia lasting >7 days, and 2 with grade 4 thrombocytopenia >7 days.

In Arm 4 (lilotomab pre-dose of 100 mg/m²), the recommended Betalutin dose for phase 2 expansion was 20 MBq/kg. Eight patients have been enrolled; the ORR is 50%. Two FL patients have had a CR. The incidences of grade 3/4 neutropenia and thrombocytopenia were 3/8 (38%) and 4/8 (50%) respectively (there was one grade 4 thrombocytopenia reported). One patient had a DLT of haematuria with thrombocytopenia (platelet count of 40 x 10^9/L) and received a platelet transfusion. A phase 2 expansion cohort is currently enrolling up to 15 patients.

Overall, Betalutin treatment was well-tolerated, with the most common adverse events (AEs) reported being neutropenia and thrombocytopenia which were transient and generally required no intervention. Bruising/bleeding episodes were reported in 3 and 4 patients respectively; only 2 patients required platelet transfusions for bleeding events in association with thrombocytopenia (one with epistaxis and one with haematuria). Overall, 23 patients (39%) developed infections, with urinary and respiratory tract infections (including nasopharyngitis) being most commonly reported (19 patients [32%]). The majority of infections were low grade in nature. The dosing regimen was generally well tolerated, with only 2 infusion reactions reported; both were related to RTX.

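### As written, grade 4 thrombocytopenia of 7 days or less with clinically significant bleeding meets no haematological DLT clause, although the same bleeding at grade 3 does

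*Combined protocol and SAP*

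**What the plan says.** The DLT definition closes Section 6.1 (Dosing regimen). Its haematological part has three alternatives:

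1. "Anemia, neutropenia or thrombocytopenia CTCAE (v4.03) grade 4 lasting >7 days";
2. "or grade 3 thrombocytopenia with clinically significant bleeding";
3. febrile neutropenia, defined by a neutrophil count and a temperature.

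The non-haematological part begins "An AE of CTCAE (v4.03) grade 3 or higher where the relationship to study treatment cannot be ruled out" and adds conditions on attribution and a 12-week window. It ends with a discretionary sentence: "Other clinically significant toxicities may also be considered to be DLTs by the Investigators and Sponsors, even if not CTCAE grade 3 or higher".

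The numbered rules earlier in the same section run on the DLT count. They are introduced by "Decisions will be based on a review of all safety data (clinical and laboratory) and are outlined as follows", and the first reads "If 0/3 patients experience a DLT (defined below), the next cohort of 3 patients will receive lilotomab 40 mg plus Betalutin 15 MBq/kg". With 1/3 the cohort is expanded. With 1/6 at 10 MBq/kg the dose is raised, and with 1/6 at 15 MBq/kg that dose is named for Phase 2. Rule 9 leaves the final recommendation to the Investigators and Sponsor after a review of the safety data. Section 9.2.2 says that there is no safety monitoring board.

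Section 2.2.2.1 gives the background rate in LYMRIT-37-01 for the 36 patients who received 40 mg lilotomab and 15 MBq/kg Betalutin: "Grade 4 neutropenia and thrombocytopenia were reported in 7 patients (19%) and 6 patients (17%) respectively". Two of the thrombocytopenia cases lasted more than 7 days.

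**The concern.** A DLT definition should not lose an event because the laboratory grade is worse. Here the bleeding clause names grade 3 alone and the grade 4 clause carries a duration condition, so a patient with lower platelets and the same bleeding can fall between them. The paragraph that follows writes grade 3 *or higher* for non-haematological events, so the protocol has that wording available and does not use it in the bleeding clause.

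Version 4.0 removed the expansion phase and made the recommended Phase 2 dose a stated secondary objective. That recommendation now rests on 6 to 12 patients, and a change of one in the DLT count can change the action taken. If the status of an event is settled only after it has been seen, by the parties who run the study, the count is no longer fully pre-specified.

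**Working it through.** **Step 1. Test the event against each clause.** The event is grade 4 thrombocytopenia, 7 days or less, with clinically significant bleeding.

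| Haematological clause | Same bleeding, grade 3 | Same bleeding, grade 4, 7 days or less |
|---|---|---|
| Grade 4 for more than 7 days | not met (grade) | not met (duration) |
| Grade 3 thrombocytopenia with bleeding | **met** | not met (grade) |
| Febrile neutropenia | not applicable | not applicable |
| Haematological DLT as written? | **yes** | **no** |

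No other section defines DLT or extends the bleeding clause to grade 4.

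**Step 2. Effect of one uncounted event on the rules.**

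- 1/3 recorded as 0/3: the cohort is not expanded. At 10 MBq/kg the dose is raised.
- 2/3 recorded as 1/3: the cohort is expanded instead of dosing being reviewed.
- 2/6 recorded as 1/6: at 15 MBq/kg that dose is named for Phase 2, instead of 3 more patients being treated at the lower dose. At 10 MBq/kg, 1/6 leads to escalation.

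**Step 3. What the documents allow on frequency.** The plan states no figure of its own to reproduce. From Section 2.2.2.1, grade 4 thrombocytopenia was 6/36, of which 2 lasted more than 7 days. Short episodes are therefore (6 − 2)/36 = 4/36 = 11.1%.

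Let *s* be the share of these episodes that come with clinically significant bleeding and meet no other DLT clause. The documents do not report *s*; I assume 10% to 100%. The per-patient rate is q = s × 4/36, and the chance of at least one event in n patients is 1 − (1 − q)^n.

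| s (assumed) | q | n = 3 | n = 6 |
|---|---|---|---|
| 10% | 1.1% | 3.3% | 6.5% |
| 25% | 2.8% | 8.1% | 15.6% |
| 50% | 5.6% | 15.8% | 29.0% |
| 100% | 11.1% | 29.8% | 50.7% |

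The last row is the upper bound: it is the chance of *any* short grade 4 thrombocytopenia, bleeding or not.

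**Step 4. Illustration of the effect on a dose decision.** A dose level is passed with 0/3, or with 1/3 followed by 0/3. For a per-patient DLT rate p, the chance is (1 − p)^3 + 3p(1 − p)^5. Let all other DLTs occur at 10% to 30% (assumed). Compare p = other rate (event left out) with p = other rate + q (event counted).

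Example with other DLTs at 20% and s = 50%:

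- left out, p = 0.200: 0.512 + 0.197 = 0.709;
- counted, p = 0.200 + 0.056 = 0.256: 0.588.

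The difference is 12 percentage points. Across other-DLT rates of 10% to 30%, it is about 2 points for s = 10%, 5 to 6 for 25%, 10 to 12 for 50% and 20 to 24 for 100%. The 4/36 belongs to 15 MBq/kg, so the calculation fits the decision on that dose best. Applying it to the 10 MBq/kg cohort borrows a rate from a higher dose.

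**The case against.** The strongest reply is that the event would rarely escape in practice.

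- A bleed of grade 3 or higher counts as a non-haematological DLT if it meets the attribution and 12-week conditions.
- The bleeding clause has no duration condition, so bleeding while platelets pass through grade 3, on the way down or up, also counts.
- The discretionary sentence fits a bleed already judged clinically significant, and the bleeding clause rests on the same kind of judgement.
- All safety data are reviewed before further dosing.

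These points stand as mitigation. The first two depend on how the event unfolds and the last two on a decision by the review team, so none gives the event a defined status. The intent was probably inclusive, but the text does not say so.

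A reader might also infer that 30% and 51% are the chances of the gap being hit. The documents do not support that. Those figures need every short grade 4 episode to bleed, and they come from single-agent Betalutin at 15 MBq/kg. Section 2.2.2.1 reports only two patients in the whole study who needed platelets for bleeding with thrombocytopenia. One had haematuria, and this appears to be the Arm 4 patient with platelets of 40 × 10^9/L whose event was already called a DLT. Taking the other as 1 of 62 enrolled gives 1 − (61/62)^3 = 4.8% in 3 patients and 1 − (61/62)^6 = 9.3% in 6. That pools arms and doses, and the patient's platelet grade is not given, so it is only a rough marker. No section reports a patient with the exact event.

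Nor do the documents show that the study's DLT count has been biased towards escalation. They show only that it could be.

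**Conclusion.** The gap is real on the wording. A grade 4 episode of 7 days or less with clinically significant bleeding is not a haematological DLT, while the grade 3 event with the same bleeding is. This follows from the text alone and needs no assumption about rates.

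The size is uncertain. The plausible range for seeing at least one such event at 15 MBq/kg is about 3% to 30% in 3 patients and 7% to 51% in 6. It rests on 4/36 from single-agent treatment, independence between patients and an assumed bleeding share of 10% to 100%. The rate at 10 MBq/kg and the rate with rituximab added are not known from the documents. The consequence of a single uncounted event is definite: in cohorts of 3 to 6, it can move the count across a decision boundary.

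This finding does not settle whether the event ought to be dose-limiting. That is a clinical question, and the point here is that the two clauses are not reconciled.

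**What to change.** In Section 6.1, reconcile the bleeding clause with the grade 4 duration clause so that the DLT status of every thrombocytopenia-with-bleeding event, at each grade and duration, is defined before the dose decision that uses it. The sponsor and investigators choose the clinical wording.

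The first patient was included in October 2018 and Version 4.0 is dated October 2021, so patients may already have been assessed under the present text. If so, record whether any such event occurred, and how it was classified, before the Phase 2 recommendation is made.

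The cost is a few words in the definition and a check of existing platelet and bleeding records. No new data are needed.

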	Two cohorts of 3-6 patients will be initially evaluated for dose limiting toxicity before determining the subsequent Betalutin dose for the remainder of the study. Dose-escalation decisions will be made by the Investigator(s) and Sponsor following review of the safety data once haematologic recovery has occurred.
	After the last dose of rituximab, vital signs, ECG (final visit only), physical examination, haematology, serum biochemistry, Adverse Drug Reaction (ADR) and Adverse Events of Special Interest (AESI) will be collected at an end of study visit that will occur at least 28 days post last administration of study treatment. Patients in survival follow-up at time of Protocol v4.0 approval can have the EOS visit at their next scheduled visit or an earlier convenient time point.
Pharmacokinetics and biodistribution	Total radioactivity measurements in blood will be performed at certain intervals until Day 28. Mandatory at Radium Hospital (Oslo, Norway) only, otherwise optional. Patients will undergo SPECT imaging at certain time points in order to measure distribution of

	Betalutin in the body and calculate absorbed radiation dose to target organs/tissues and tumours.
Biomarker assessments	Biomarkers assessments including CD20 and CD37 expression in tumour tissue biopsy and immunophenotyping of circulating lymphocyte subsets (absolute cell counts), will be performed at various time points throughout the study
Other biomarker studies on additional samples	Biomarkers including but not exclusive to MRD (blood) and gene expression changes related to disease treatment in tumour tissue (archival or newly collected biopsy at screening, relapse or disease progression), will be assessed at various time points throughout the study. Patient's major histocompatibility complex (MHC) class I/II haplotype will be defined using peripheral blood (DNA) or saliva (DNA). Anti-tumour T-cell responses will be explored by flow cytometry after co-culture of peripheral mononuclear cells (blood) and autologous lymphoma cells (biopsy and/or needle aspirate), and other biomarkers at selected time points throughout the study at Radium Hospital (Oslo, Norway) only.
Statistical methods and data analysis	The safety analysis population will include all patients who received at least one dose of any study drug.

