## 8.1. Screening Period

During the initial screening visit at the study site, the Investigator must inform each prospective study patient of the nature of the study, explain the potential risks, and obtain written informed consent from the patient prior to performing any study-related screening procedures. Once the informed consent document has been signed, the patient may undergo the screening procedures.

Pre-treatment period is defined from start of screening to the administration of the first RTX dose.

The tests and assessments outlined in Table 8-1 will be performed within 4 weeks prior to RTX infusion (pre-treatment period).

 Table 8-1
 Procedure and assessments at Screening Visit (Visit 1)

Assessment or Procedure	Explanation
Obtain Informed Consent	The patient must be fully informed about the study and sign the Informed consent form (ICF). The ICF needs to be signed before any treatment or study-related procedures are initiated.
Demographics	Date of birth, sex, ethnic origin, race should be recorded
Inclusion/exclusion criteria	See Section 5
Medical History	Record details of all previous or concomitant conditions or surgical procedures
Urinalysis	To check for urinary infection
Concomitant medication/therapy	If the patient is receiving any medication for conditions mentioned on the Medical History page, details need to be recorded on the Concomitant therapies record
Physical examination	Check and describe any significant abnormal physical examinations findings (heart, lung, abdomen, general, skin, oral cavity, chest and lymph nodes). Any abnormalities will be recorded on Medical History record
Height and weight	Record height and weight details
Vital signs	Systolic/diastolic blood pressure, heart rate, and body temperature

12-lead ECG	A copy of the medically reviewed ECG page will be
	signed, dated and interpreted before storing in the patient
	file
ECOG	ECOG performance status for study inclusion
Haematology	Including haemoglobin, platelet count, white blood cell
	count and differential (absolute count of neutrophils,
	lymphocytes, monocytes, eosinophils and basophils)
Serum biochemistry	Including sodium, potassium, calcium, magnesium,
	creatinine, urea, uric acid, alkaline phosphatase (ALP),
	aspartate transaminase (ASAT), alanine transaminase
	(ALAT), lactate dehydrogenase (LDH), gamma-
	glutamyltransferase (GGT), glucose, total bilirubin and
	albumin

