#### 8.2. Treatment Period

Patients will undergo the following visits during the treatment period.

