### 9.2.2. Safety review

A safety monitoring board will not be used for this study. Instead, Nordic Nanovector will have frequent access to the safety and other clinical data and will host Investigator teleconferences on a regular basis during the study to review the ongoing safety of the patients.

After the first 3 patients are enrolled, and once haematological recovery has occurred, Nordic Nanovector will convene a teleconference with the Investigators to discuss and evaluate all of the safety data before dosing additional patients.

The following safety data will be collected and evaluated (see Section 9.2.6):

- AFs
- Laboratory variables: haematology, serum biochemistry and immunoglobulin levels data
- Immunogenicity
- Vital signs
- 12-lead ECGs
- Physical examination
- Long-term toxicity

The time points for all assessments are shown in the Schedule of activities (Section 1.2) AEs will be graded and recorded throughout the study according to NCI CTCAE version 4.03.

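### A cohort can be scored DLT-free on dosing and blood-count recovery alone, before the 12-week non-haematological DLT window has closed

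*Combined protocol and SAP*

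**What the plan says.** **When a cohort may be scored.** Section 6.1 sets one condition: "Patients must have received all doses of study drug and have had an adequate period of follow-up (i.e. having achieved haematological recovery to" grade 2 or less. A patient who meets it qualifies "to be considered evaluable for a dose escalation decision or to determine the dose for further Phase 2 studies". Adequate follow-up is therefore defined by blood-count recovery alone. The synopsis (Section 1.1, safety assessments) gives the same trigger: "Dose-escalation decisions will be made by the Investigator(s) and Sponsor following review of the safety data once haematologic recovery has occurred". So does Section 9.2.2, which places the first review before additional patients are dosed: "After the first 3 patients are enrolled, and once haematological recovery has occurred".

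**What counts as a DLT.** The haematological criteria in Section 6.1 carry no time limit. The non-haematological criterion covers an event of grade 3 or higher, not attributable mainly to other causes, "that occurs within the first 12 weeks of treatment".

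**When treatment starts.** The DLT definition names no start day. Section 8.1 says "Pre-treatment period is defined from start of screening to the administration of the first RTX dose". Section 8.2 opens with "Patients will undergo the following visits during the treatment period", and the first visit under it is the RTX dose at Day -14. Section 6 lists RTX as a study drug.

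**The final dose.** Rule 9 of Section 6.1 rests the phase 2 recommendation on a decision made "after a review of the available safety data".

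**The concern.** The event being counted and the time of counting do not match. A team that follows the plan exactly can record 0/3 while a patient is still inside the period in which a non-haematological DLT would count. No section sets a minimum follow-up, and none says that a DLT arising after a call is added to that cohort's total or that the call is reopened.

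In cohorts this small, one event changes the branch taken: 0/3 escalates and 1/3 expands the cohort; 1/6 clears the dose and 2/6 at 15 MBq/kg sends patients back to 10 MBq/kg. The exposed decisions are the escalation and expansion calls, which fix the dose for the next patients in the first study of this combination.

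Blood counts do not detect the events in question. Weeks 5-7 and 9-11 are laboratory visits whose tables list only haematology and biochemistry. Adverse events are collected continuously, but the visit tables schedule their recording at Day 28, Week 8 and Week 12. A call at Day 49 (Week 7) would rest on the scheduled enquiry at Day 28, and one at Day 63 (Week 9) on the enquiry at Week 8.

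**Working it through.** The plan gives no figure for this interval. The related figure it does give, 6 to 12 patients, reproduces as 2 cohorts x 3 = 6 and 2 x 6 = 12.

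**Inputs**
- Window length: 12 weeks = 84 days (Section 6.1).
- Window start: Day -14 on the natural reading (Sections 8.1 and 8.2), or Day 0 if counted from Betalutin.
- Last induction RTX: Day 28 (Section 6.1).
- Nadir: 5-7 weeks after Betalutin, i.e. Day 35-49 (Section 7.2).
- Grade 3/4 cytopenias resolve by 3 months in most patients (Section 2.4).
- Recovery day: not given. Assumed Day 49-63, about two weeks after the nadir.
- RTX precedes Betalutin by 14 days (Section 6.1).

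**Step 1: window still open at the call** = (start day + 84) - recovery day, for the last-treated patient of the cohort.
- Day -14 start, closing at Day 70: 70 - 63 = 7 days; 70 - 49 = 21 days (1-3 weeks).
- Day 0 start, closing at Day 84: 84 - 63 = 21 days; 84 - 49 = 35 days (3-5 weeks).

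**Step 2: window still open when the escalated Betalutin is injected.** If the next patient receives RTX on the day of the call, Betalutin follows 14 days later, at Day 63-77 of the last-treated patient (the Day -14 visit has a tolerance of ±2 days).
- Closing at Day 70: 70 - 63 = 7 days; 70 - 77 is below zero, so 0. Range 0-7 days.
- Closing at Day 84: 84 - 77 = 7 days; 84 - 63 = 21 days. Range 7-21 days.

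**Step 3: extremes**
- Recovery at about 3 months (Day 84): no gap on either start day.
- A patient who never exceeds grade 2, read literally, is evaluable after the Day 28 RTX: 70 - 28 = 42 days, or 84 - 28 = 56 days, at the call. Weekly sampling until recovery after nadir values (schedule of activities, footnote 17) and the nadir timing in Section 7.2 count against deciding that early.

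**Step 4: are the uncounted events likely to come late?**
- Both sepsis cases in LYMRIT-37-01 occurred with neutropenia around Day 40 (Section 2.2.2.1), and Section 2.4 links infections to neutropenia. A recovery trigger tends to capture these.
- Section 2.3.3 names infection from prolonged lymphopenia only as a possibility.
- The nearest regimen, radioimmunotherapy followed by weekly RTX, had one grade 3 serum sickness-like event among 55 patients (1/55 = 1.8%; Section 2.3.3). Its onset day is not given.

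The documents give no onset distribution for non-haematological DLTs, so the change in the 3+3 rule's operating characteristics cannot be calculated from them.

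**The case against.** The strongest reply is that little exposure hangs on the gap. The 14-day RTX lead-in uses up most or all of the remaining window before anyone receives the escalated Betalutin. The injected activity is calculated on the day of injection (Section 6.3.1), serious events reach the sponsor within 24 hours (Section 9.2.5.1), and the sponsor has frequent data access and regular teleconferences (Section 9.2.2). The escalated dose, with the same lilotomab pre-dose, was given to 36 patients as a single agent (Section 4.3). Investigators and sponsor may also class other significant toxicities as DLTs. For the phase 2 dose, rule 9 lets later events in.

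This stands as an argument about size, and the 0-7 and 7-21 day figures reflect it. It does not supply the missing rule. Reviewing all safety data covers what is known at the call, not events still to come, and nothing says what a late event would change.

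Two further defences are weaker. Reading all doses to include maintenance RTX to Month 24 would close the window, but would make the recovery triggers in Sections 1.1 and 9.2.2 unworkable. The worry that a patient progressing before Week 12 could never be scored is largely met: Section 9.2.4 requires adverse event reporting to 12 weeks after Betalutin, and Section 7.2 asks sites to continue safety monitoring after progression.

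**Conclusion.** The mismatch is real, lies in the stated rule, and should be corrected. On an assumed recovery at Day 49-63, the call precedes window closure by 1-3 weeks (Day -14 start) or 3-5 weeks (Day 0 start), with about 0-7 or 7-21 days open at the escalated injection. The recovery day is an assumption; later recovery shrinks the gap to nothing.

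A reader might infer that the escalation rule is materially looser than it looks, by treating a late share of all DLTs as unobserved. The documents do not support that. The listed haematological DLTs involve grade 3-4 cytopenias or low neutrophils with fever, which a recovery trigger is built to see through. Only non-haematological events can fall in the gap, and the documented infections cluster with neutropenia. The effect on the 3+3 rule is therefore not derivable and probably small. Nor do the documents show that the phase 2 recommendation would be wrong, since rule 9 can take in later events.

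**What to change.** In Sections 1.1, 6.1 and 9.2.2:

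1. Count a patient as DLT-free only after both haematological recovery to grade 2 or less and closure of the existing 12-week non-haematological window.
2. Name one start day for that window, Day -14 or Day 0, without lengthening it. Leave the haematological criteria as they are.
3. Count a DLT as soon as it occurs; no waiting is needed for a patient who has one.
4. Confirm adverse event status at the existing Week 12 contact (Day 84 ± 7, i.e. Day 77-91), on or after Day 84 if the start is Day 0. For patients who progress earlier, use the reporting already required to 12 weeks after Betalutin.
5. Add any in-window DLT arising after a call to that cohort's count, and revisit the decision before the next Betalutin injection.

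**Cost.** Wording in three sections, with no new assessments. With recovery at Day 49-63, waiting for closure delays each decision by about 1-3 weeks on a Day -14 start or 3-5 weeks on a Day 0 start. For a patient who never exceeds grade 2, the delay is up to 6 weeks (42 days) or 8 weeks (56 days). On a Day -14 start, waiting for the Week 12 visit itself adds at least one week (77 - 70 = 7 days). This delay matters in a trial already cut back for slow recruitment, and is a reason to choose the start day deliberately.
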